3.8.4. Dose Adjustment for Hematologic Toxicity

3.8.4.1. For subjects with lymphoma and multiple myeloma:

The treatment may be held for 2 weeks if:

- neutrophil and platelet count did not recover to neutrophils $\geq 0.5 \times 10^9/L$ and platelets $\geq 25 \times 10^9/L$

The treatment may resume as soon as count recovery has occurred (i.e., neutrophils ≥ 0.5 and platelets $\geq 25 \times 10^9/L$).

When the treatment resumes, the dose may be adjusted based on platelet count, i.e., dose can be reduced by 1 or 2 dose levels when the platelet count $\leq 25 \times 10^9/L$ (G4 thrombocytopenia) and it is not attributed to the disease. If a subject has persistent G4 thrombocytopenia for 4 weeks not attributed to disease or requires platelet transfusions for bleeding in the absence of the disease, the subject will be withdrawn from the study.

For non drug-related hematologic toxicity institutional guidelines for re-starting may be followed.

3.8.4.2. For subjects with solid tumors:

Thrombocytopenia:

- Grade 1 & 2 (platelet count \geq 50,000): Continue dosing at same dose level with weekly or more frequent monitoring as necessary.

- Grade 3 (platelet count between 25,000 to <50,000): After discussion with medical monitor and using sound clinical judgement, continue at same dose or consider dose interruption until count recovery to Grade 2 or less. Monitor platelet count at a minimum of twice weekly.

- Grade 4 (platelet count below 25,000): Interrupt study medication and monitor platelet count every 2-3 days. If platelet counts recover to Grade 2, discuss with medical monitor resuming treatment at the same or adjusted dose based on sound clinical judgement. Platelet transfusion is allowed based on institutional guidelines. In case of platelet transfusion, hold drug for at least 7 days from day of transfusion, and if platelet counts recover to Grade 2 consider initiating treatment at a lower dose using sound clinical judgement and after consulting with the GSK medical monitor. Discontinue treatment if drug has to be held for >14 days or greater than 2 dose reductions required.

3.9. Guidelines for Events of Special Interest and Dose Modifications**3.9.1. Dose Modifications**

Dose reductions for GSK2816126 will depend on their starting dose. If a subject has a dose reduction for toxicity the dose will be reduced by one dose level. Approval from the GSK Medical Monitor is required to restart a dose after 14 days of dose interruption. Following a dose reduction subjects may be re-escalated to a higher dose level with the approval of the GSK Medical Monitor if the toxicity has resolved.

4. INVESTIGATIONAL PRODUCT

The term 'study treatment' is used throughout the protocol to describe the investigational product received by the subject as per the protocol design.

4.1. Description of Investigational Product

Table 5 Investigational Product

Product name:	GSK2816126 Injection, 15 mg/mL, 30 mL vial with 25 mL fill volume
Formulation description:	Solution containing 15 mg/mL GSK2816126 in water for Injection, methanesulfonic acid, Captisol and acetic acid
Dosage form:	A solution stored at 2-8°C, protected from light
Unit dose strength(s)	15 mg/mL
Route/Regimen	Delivered as an intravenous solution over 2 - 4 hours Study drug can be diluted into saline or dextrose for a final volume of 250ml at ambient temperature and normal room lighting up to 12 hours prior to infusion. PVH, PE and PA bags and tubing are all acceptable
Physical description:	A clear, pale yellow coloured solution, essentially free from visible particles of foreign matter

GSK2816126 will be provided to sites by GSK. The contents of the label will be in accordance with all applicable regulatory requirements.

4.2. Preparation/Handling/Storage of GSK2816126 GSK Investigational Product

Preparation

Under normal conditions of handling and administration, IP is not expected to pose significant safety risks to site staff. A Material Safety Data Sheet (MSDS) describing the occupational hazards and recommended handling precautions will be provided to site staff if required by local laws or will otherwise be available from GSK upon request.

In the case of unintentional occupational exposure notify the study monitor, the GSK Medical Monitor and/or the study manager.

Take adequate precautions to avoid direct eye or skin contact and the generation of aerosols or mists.

Refer to the Study Procedures Manual (SPM) for detailed procedures for the disposal and/or return of unused study treatment(s).

Storage

GSK2816126 must be stored in a secure area under the appropriate physical conditions for the product. Access to and administration of the GSK2816126 will be limited to the investigator and authorized site staff. GSK2816126 must be dispensed or administered only to subjects enrolled in the study and in accordance with the protocol.

GSK2816126 is to be stored protected from light in 30 mL Type 1 glass vials, at a temperature range of [2°C/36°F to 8°C/46°F]. Maintenance of a temperature log (manual or automated) is required.

4.3. Product Accountability

In accordance with local regulatory requirements, the investigator, designated site staff, or head of the medical institution (where applicable) must document the amount of IP dispensed and/or administered to study subjects, the amount returned by study subjects, and the amount received from and returned to GSK, when applicable. Product accountability records must be maintained throughout the course of the study. Refer to the SPM for further detailed instructions on product accountability.

4.4. Treatment Compliance

When subjects are dosed at the study site, they will receive study treatment directly from the investigator or designee, under medical supervision. The date and time of each dose administered in the clinic will be recorded in the source documents. The dose of study treatment and study participant identification will be confirmed at the time of dosing by a member of the study site staff other than the person administering the study treatment.

GSK2816126 will be intravenously administered to subjects at the study site. Administration will be documented in the source documents and reported in the electric case report form (eCRF). Treatment start and stop dates, including dates for treatment delays and/or dose reductions will also be recorded in the eCRF.

4.5. Treatment of Investigational Product Overdose

In the event of an overdose (defined as administration of more than the protocol-specified dose) of GSK2816126 the investigator should:

- Contact the GSK Medical Monitor immediately
- Closely monitor the subject for AEs/SAEs and laboratory abnormalities until GSK2816126 can no longer be detected systemically
- Obtain a plasma sample for PK analysis within 24 hours from the date of the last dose of study treatment if requested by the GSK Medical Monitor (determined on a case-by-case basis)
- Document the quantity of the excess dose as well as the duration of the overdosing in the eCRF

Decisions regarding dose interruptions or modifications will be made by the investigator in consultation with the GSK Medical Monitor based on the clinical evaluation of the subject.

5. STUDY POPULATION

5.1. Number of Subjects

A maximum of approximately 250 subjects will be enrolled. See Section [12.2](#) for sample size assumptions.

The number of dose levels and the level at which the RP2D [or maximum tolerated dose (MTD) or maximum feasible dose (MFD)] is reached cannot be determined in advance. An adequate number of subjects will be enrolled into the study to establish the recommended dose(s) for further study. It is estimated that approximately 40 subjects will be enrolled into Part 1 dose-escalation of the study. Additionally in Part 1 cohort expansion, approximately 27 GCB-DLBCL subjects and approximately 15 solid tumor subjects containing EZH2 inhibitor sensitizing mutations or subjects with prostate cancer will be enrolled.

Approximately up to 168 subjects will be enrolled in Part 2 in five expansion cohorts: two GCB-DLBCL cohorts with up to 32 subjects from the EZH2 wild-type population, and up to 32 subjects from the EZH2 mutation positive population, and two tFL cohorts with up to 32 subjects from the EZH2 wild-type population and up to 32 subjects from the EZH2 mutation positive population and up to 40 subjects in the MM cohort. Additional subjects/cohorts may be enrolled to allow for evaluation of additional dose levels.

In Part 1 (dose-escalation) of the study, if subjects prematurely discontinue, additional subjects may be enrolled and assigned to the same treatment sequence at the discretion of the Sponsor in consultation with the investigator. Subjects will not be replaced in Part 2 (expansion cohort) of the study.

5.2. Subject Selection Criteria

5.2.1. Part 1 Inclusion Criteria

Deviations from inclusion criteria are not allowed because they can potentially jeopardize the scientific integrity of the study, regulatory acceptability or subject safety. Therefore, adherence to the criteria as specified in the protocol is essential.

Subjects eligible for enrollment in the study must meet all of the following criteria:

1. Provided signed written informed consent.
2. Males and females ≥ 18 years of age (at the time consent is obtained).
3. Tumor type criteria

- Relapsed/refractory non-Hodgkin's lymphoma (NHL) that meets the following criteria:
 - Germinal Center B cell Diffuse large B cell lymphoma (GCB-DLBCL) relapsed or refractory to at least one prior regimen (e.g., rituximab, cyclophosphamide, doxorubicin, vincristine, prednisone [R-CHOP]) AND not a candidate for standard salvage regimens or autologous or allogeneic stem cell transplant. Local confirmation of lymphoma subtype GCB-DLBCL is allowed for enrollment but must be confirmed through central laboratory testing.
- Solid tumors that meet the following criteria:
 - Measurable disease by RECIST 1.1 in at least 1 site
 - For Castrate Resistant Prostate Cancer (CRPC) measurable disease can also include PSA level (see below)
 - Disease progression with the last line of therapy and at least one prior standard of care regimens, or tumor for which there is no approved therapy, or for which standard therapy is unsuitable or refused.
 - Mutation Status:
 - Solid tumor types, other than prostate, must have one of the following EZH2 inhibitor sensitizing mutations as determined via local testing:
 - An activating mutation in EZH2 (Y641F/C/S/H/N, A677V/G, and/or A687V)
 - Loss of a component of the SWI/SNF complex, including, but not limited to, ARID1A, SMARCB1 (aka SNF5/INI1/BAF47), SMARCA4 (aka BRG1), or PBRM1 (aka PB1) as determined by molecular testing (bi-allelic loss or mutation) or immunohistochemistry
 - Loss of BAP1 (ubiquitin carboxy-terminal hydrolase) as determined by molecular testing (bi-allelic loss or mutation) or immunohistochemistry
 - CRPC subjects:
 - Must have measurable disease by either:
 - RECIST1.1 (see [Appendix 5](#)) or,
 - A minimum PSA of 5 ng/mL
 - Disease progression on last line of therapy and must have progressed on abiraterone, enzalutamide, or taxane chemotherapy
 - Subjects may continue GnRH agonists
 - Small cell prostate cancer is eligible

4. For all subjects: Availability of archival tissue, or willingness to undergo fresh biopsy if archival tissue is not available as described in Section 7.6.1.1, Section 7.6.1.2 and Section 7.6.5.
5. Must have a pre-existing central venous access such as a port, Hickmann catheter, or a peripherally inserted central catheter (PICC line) or be willing and able to have one inserted.
6. ECOG Performance Status of 0 or 1 (see [Appendix 2](#)).
7. Men with a female partner of childbearing potential must have either had a prior bilateral vasectomy with resultant azoospermia, bilateral orchiectomy, or must agree to use one of the contraception methods listed in Section 10.1 from the time of the first dose of study medication until at least 2 weeks (14 days) after the last dose of study treatment due to long elimination phase.
8. A female subject is eligible to participate if she is of:
 - Non-childbearing potential as defined in Section 10.1.1
 - Child bearing potential as defined in Section 10.1.1 and agree to use effective contraception, as defined in Section 10.1, for an appropriate period of time (as determined by the product label) prior to the start of dosing to sufficiently minimize the risk of pregnancy and for at least 2 weeks (14 days) following the last dose of study treatment. Women of childbearing potential must have a negative serum pregnancy test within 7 days of first dose of study treatment followed by negative urine or serum pregnancy test once every 4 weeks (prior to next dose cycle) thereafter.
9. Adequate organ system function as defined below:

System	LABORATORY VALUES
Hematologic	
ANC	≥1.2 x 10 ⁹ /L
Hemoglobin	≥9 g/dL
Platelets	≥75x 10 ⁹ /L
PT/INR and PTT	≤1.5 x ULN
Hepatic	
Albumin	≥2.5 g/dL
Total bilirubin	≤1.5 times ULN
AST and ALT	≤2.5 times ULN without liver metastases ≤5 times ULN if documented liver metastases
Renal	
Calculate Creatinine Clearance ^{a, b}	≥50 mL/min
Reproductive/Endocrine for CRPC only	
Testosterone	<50 ng/dL (only for subjects with CRPC)
Cardiac	
Left Ventricular Ejection Fraction (LVEF)	≥LLN (minimum of 50% LVEF) by ECHO or MUGA ^c

Abbreviation(s): ANC, absolute neutrophil count; ALT, alanine aminotransferase; AST, aspartate aminotransferase; ECHO, echocardiogram; INR, international normalization ratio, MUGA, multigated (radionuclide) angiogram; PT, prothrombin time, PTT, partial thromboplastin time, ULN, upper limit of normal, LLN, lower limit of normal.

- a. Calculated by Cockcroft-Gault formula
- b. For MM subjects, adequate renal function is defined as calculated creatinine clearance ≥ 30 mL/min.
- c. ECHO is the preferred method and should always be used if available

NOTE: Laboratory results obtained during Screening should be used to determine eligibility criteria. In situations where laboratory results are outside the permitted range, the investigator may opt to retest the subject and the subsequent within range screening result may be used to confirm eligibility.

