5.2.2. Part 2 Inclusion Criteria

1. In addition to inclusion criteria listed for Part 1, Part 2 will enroll **GCB-DLBCL, tFL and MM subjects only**.
 - Relapsed and/or refractory MM or tFL that have failed prior standard therapy and for which there is no standard salvage regimen
2. Lymphoma subjects will be required to undergo EZH2 mutation testing. This will require availability of archival tissue, or willingness to undergo fresh biopsy, for central testing of EZH2 mutation status.
3. Based on the results of the mutation test, lymphoma subjects may be enrolled in one of four cohorts:
 - GCB-DLBCL EZH2 mutant cohort:
 - Tumors must contain one, or more, of the following EZH2 activating mutations: Y641F; Y641N; Y641S; Y641H; Y641C; A677G; and/or A687V
 - GCB-DLBCL EZH2 wild type cohort:
 - Tumors that do not contain one of the above mutations
 - Subjects with tumors harboring EZH2 mutations other than the seven outlined above will be enrolled in the EZH2 wild type cohort
 - tFL EZH2 mutant cohort:
 - Tumors must contain one, or more, of the following EZH2 activating mutations: Y641F; Y641N; Y641S; Y641H; Y641C; A677G; and/or A687V
 - tFL EZH2 wild type cohort:
 - Tumors that do not contain one of the above mutations
 - Subjects with tumors harboring EZH2 mutations other than the seven outlined above will be enrolled in the EZH2 wild type cohort

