7.2. Demographic/Medical History and Baseline Assessments

The following demographic parameters will be captured during Screening: date of birth (in accordance with local data protection legislation), gender, race and ethnicity.

Baseline (Screening) assessments obtained will include:

- Complete physical examination, including height (in cm) and weight (in kg)
- Vital signs (BP, temperature, respiratory rate, pulse rate)
- Past and current medical conditions, alcohol and tobacco use
- ECOG performance status
- Lactate dehydrogenase (LDH) level
- Disease characteristics for all subjects including:
 - Date of initial diagnosis
 - Initial diagnosis tumor histology
 - ECOG performance status at initial diagnosis
 - Tumor location involvement at initial diagnosis
 - Previous cancer treatments (e.g., cytotoxics, radiotherapy, maintenance, surgery)
 - Ongoing toxicities related to previous treatment
 - Best response to previous treatment(s)
 - Date of relapse/refractory diagnosis
 - Tumor histology (if relapse/refractory tumor biopsy completed). For Part 2 subjects, tumor biopsy is mandatory for inclusion. See Section [7.6.5](#).
 - ECOG performance score at time of first relapse/refractory diagnosis (as applicable)
- Diagnostic quality CT imaging with contrast within 28 days of first dose of study treatment identifying nodes, nodal masses, spleen/liver nodules and, if applicable measurable extra nodal disease. Diagnostic quality CT imaging is the preferred method of disease assessment. If PET/CT has been performed within this window, diagnostic CT will not be required. See Section [7.7](#) for further information.
- If completed and will be utilized for assessment of disease, PET imaging within 28 days of first dose of study treatment. Images may be obtained from standalone PET scanners or via combination PET/CT scanners. Standalone PET does not replace diagnostic CT. See Section [15.4](#) for further information.
- For NHL, unilateral or bilateral bone marrow biopsy within 35 days prior to commencing study therapy.
- Clinical laboratory tests: hematology, clinical chemistry, coagulation parameters

- Serum beta-human chorionic gonadotropin (β -HCG) pregnancy test for female subjects of childbearing potential only
- 12-lead ECG
- ECHO or MUGA
- Review of concomitant medications
- Baseline assessments for subjects with GCB-DLBCL
 - Ann Arbor stage of initial diagnosis for NHL
 - Ann Arbor stage of relapse/refractory diagnosis for NHL

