12.3.1. Analysis Populations

All Subjects Population: This will consist of all subjects who received at least one dose of study treatment. Safety and clinical activity analyses will be evaluated based on this population.

The PK Concentration Population: This will consist of those subjects in All Subjects Population for whom a PK sample is obtained and analyzed.

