To be assigned a status of partial response, all changes must be confirmed by repeat assessments performed no less than four weeks after the criteria for PR were met.

1. At least a 50% decrease from baseline in the SPD of up to six of the largest dominant nodes or nodal masses.

2. No increase in the size of the liver or the spleen. No unequivocal progression in any nonmeasurable or nondominant site.
3. Splenic and hepatic nodules must regress by $\geq 50\%$ in SPD compared to baseline. If only a single nodule/lesion, it must regress by $\geq 50\%$ in the greatest transverse diameter compared to baseline.
4. With the exception of splenic and hepatic nodules, involvement of other organs is accessible and no measureable disease should be present.
5. Bone marrow assessment is not relevant for determination of a PR if the sample was positive prior to treatment. However, if positive, the cell type should be specified. Subjects who achieve CR criteria above, except for persistent morphologic bone marrow involvement will be considered partial responders. When the bone marrow was involved before therapy and a clinical CR was achieved, but no bone marrow assessment after therapy, subjects must be considered partial responders.
6. No new sites of disease must be observed.
7. When performed, positron emission tomography (PET) must be positive in at least one previously involved site.

Stable Disease

Neither sufficient shrinkage to qualify for a CR or PR nor sufficient increase to qualify for progressive disease taking as reference the smallest SPD since the treatment started.

When performed, PET should be positive at prior sites of disease with no new areas of involvement on the CT or PET.

Relapsed Disease (after CR)/Progressive Disease (after PR, SD)

Criteria for determining PD for new lesions and target lesions are shown in [Table 19](#):

Table 19 Criteria for determining PD for new lesions and target lesions

	Nodes	Extranodal ('liver/spleen' & 'other' categories)

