Ic. Follow-up Assessments for Subjects Permanently Discontinued from Study Treatment

Refer to Section 8.3.1.1 and the Time and Events Tables found in the protocol for follow-up assessment of subjects who are to be followed up for disease progression and/or survival after permanently discontinue from study treatment.

Id. Assessment of Subject Completion

If the last radiographic assessment was more than 8 weeks prior to withdrawal from study and progressive disease has not been documented, a disease assessment should be obtained at the time of withdrawal from study.

II. Guidelines for Evaluation of Disease

IIa. Measurable and Non-measurable Definitions

Measurable lesion:

A non nodal lesion that can be accurately measured in at least one dimension (longest dimension) of

- ≥ 10 mm with MRI or CT when the scan slice thickness is no greater than 5mm. If the slice thickness is greater than 5mm, the minimum size of a measurable lesion must be at least double the slice thickness (e.g., if the slice thickness is 10 mm, a measurable lesion must be ≥ 20 mm).
- ≥ 10 mm calliper/ruler measurement by clinical exam or medical photography.
- ≥ 20 mm by chest x-ray.

Additionally lymph nodes can be considered pathologically enlarged and measurable if

- ≥ 15 mm in the short axis when assessed by CT or MRI (slice thickness recommended to be no more than 5mm). At baseline and follow-up, only the short axis will be measured [Chung, 2010; Eisenhauer, 2009].

Non-measurable lesion:

All other lesions including lesions too small to be considered measurable (longest diameter <10 mm or pathological lymph nodes with ≥ 10 mm and <15 mm short axis) as well as truly non-measurable lesions, which include: leptomeningeal disease, ascites, pleural or pericardial effusions, inflammatory breast disease, lymphangitic involvement of the skin or lung, abdominal masses/abdominal organomegaly identified by physical exam that is not measurable by reproducible imaging techniques [Eisenhauer, 2009].

Measurable disease: The presence of at least one measurable lesion. Palpable lesions that are not measurable by radiologic or photographic evaluations may not be utilized as the only measurable lesion.

Non-Measurable only disease: The presence of only non-measurable lesions. Note: non-measurable only disease is not allowed per protocol.

III. Response Criteria

IIIa. Evaluation of target lesions

Definitions for assessment of response for target lesion(s) are as follows:

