15.6. Appendix 6: Response Criteria for Multiple Myeloma

Consensus Recommendations [Rajkumar, 2011] for the Uniform Reporting of Clinical Trials: Report of the International Myeloma Working Group (IMWG) Consensus Panel

Response Criteria [Durie, 2006]

sCR (stringent complete response):

Complete response as defined below plus:

- normal free light chain (FLC) ratio and
- absence of clonal cells in bone marrow by immunohistochemistry or 2-4 color flow cytometry.

CR (complete response):

- Negative serum and urine immunofixation, and
- Disappearance of any soft tissue plasmacytomas, and
- $\leq 5\%$ plasma cells in bone marrow.

VGPR (very good partial response):

- Serum and urine M-component detectable by immunofixation but not on electrophoresis **OR**
- 90% or greater reduction in serum M-component plus urine M-component $< 100\text{mg}/24\text{h}$.

PR (partial response):

- $\geq 50\%$ reduction of serum M-protein and reduction in 24 hour urinary M-protein by $\geq 90\%$ or to $< 200\text{mg}/24\text{h}$, and
- If the serum and urine M-protein are not measurable, a $\geq 50\%$ decrease in the difference between involved and uninvolved free light chain levels is required in place of the M-protein criteria. If serum and urine M-protein are not measurable, and serum free light chain assay is also not measurable, $\geq 50\%$ reduction in bone marrow plasma cells is required in place of M-protein, provided baseline bone marrow plasma cell percentage was $\geq 30\%$, and
- In addition to the above listed criteria, if present at baseline, a $\geq 50\%$ reduction in the size of the soft tissue plasmacytomas is also required.

MR (minimal response):

- $\geq 25\%$ but $\leq 49\%$ reduction of serum M-protein and reduction in 24 hour urinary M-protein by 50% to 89%, AND
- If present at baseline, 25% to 49% reduction in the size of soft tissue plasmacytomas is also required.
- No increase in size or number of lytic bone lesions (development of compression fracture does not exclude response).

SD (stable disease):

- Not meeting criteria for CR, VGPR, PR, MR or Progressive Disease.

Progressive Disease:

Requires any one or more of the following:

- Increase of $\geq 25\%$ from lowest response value in any one or more of the following:
 - serum M-component (absolute increase must be ≥ 0.5 g/dl), or
 - urine M-component (absolute increase must be ≥ 200 mg/24h), or

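### Measurable disease is an entry condition only for solid tumors, so the GCB-DLBCL, tFL and MM cohorts with a formal ORR test may admit subjects with little or no route to PR, and their designs have almost no spare power

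*Protocol*

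**What the plan says.** **Eligibility.** In Section 5.2.1, criterion 3, solid tumors must have "Measurable disease by RECIST 1.1 in at least 1 site"; castrate-resistant prostate cancer may qualify by PSA instead. Section 12.1.1 makes that cohort descriptive. The lymphoma line of the same criterion is "Germinal Center B cell Diffuse large B cell lymphoma (GCB-DLBCL) relapsed or refractory to at least one prior regimen", followed by conditions on salvage therapy, transplant and subtype confirmation. Section 5.2.2 adds for Part 2 "Relapsed and/or refractory MM or tFL that have failed prior standard therapy and for which there is no standard salvage regimen". Neither line mentions measurable disease, and the synopsis matches both. Section 5.2.1 allows no deviations from these criteria.

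**Other places that might close the gap.** Appendix 5 says that "non-measurable only disease is not allowed per protocol", but that is the RECIST appendix, which Section 7.7 assigns to solid tumors and prostate cancer. Section 7.2 lists, among what baseline CT should identify, "spleen/liver nodules and, if applicable measurable extra nodal disease"; that is an assessment, not an entry rule.

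**Response definitions.** Lymphoma PR in Appendix 4 starts from "At least a 50% decrease from baseline in the SPD of up to six of the largest dominant nodes or nodal masses". In Appendix 6, MM PR is judged on M-protein, then on free light chains (FLC) if M-protein is not measurable, then on marrow plasma cells, "provided baseline bone marrow plasma cell percentage was" at least 30%. Table 6 has scheduling notes for non-secretory MM, so such subjects are foreseen.

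**Who is counted.** Section 12.3.1 defines the set of all treated subjects and adds "Safety and clinical activity analyses will be evaluated based on this population". The evaluability rule for the interim looks in Section 3.3.7 does not depend on measurable disease. Section 5.1 rules out replacement in Part 2.

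**The concern.** The entry condition that makes a response scorable is attached to the cohort without a hypothesis test and is absent from the cohorts with one. Two kinds of subject satisfy the criteria yet have little or no route to PR: lymphoma with no measurable node, mass or liver/spleen nodule, and non-secretory MM with unmeasurable FLC and baseline marrow plasma cells below 30%. They stay in the denominator and have essentially only CR to contribute to the numerator.

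At stake is the reading of the response counts against Tables 16, 17 and 18. Diluting the ORR moves an active cohort towards the futility column. In Part 1 the result also bears on whether Part 2 opens.

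**Working it through.** **Inputs.** Boundaries: Tables 16, 17 and 18. Rates: 20% against 40% for lymphoma and 10% against 25% for MM (Section 12.1). Cohort sizes: 13-27, 10-32 and 14-40. The share q of subjects unable to respond is an assumption; the protocol gives no value.

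**Step 1: reproduce the plan.** Follow the number of responders one subject at a time with response probability p. From the minimum size onward, stop at the futility column or, in Table 16, at the efficacy column. Count success if an efficacy boundary is crossed or the final futility number is exceeded.

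| | Table 16 | Table 17 | Table 18 |
|---|---|---|---|
| Type I error, exact | 0.0865 | 0.0660 | 0.0721 |
| Type I error, stated | 0.087 | 0.066 | 0.072 |
| Power, exact | 0.8031 | 0.8007 | 0.8142 |
| Power, stated | 0.803 | 0.801 | 0.814 |

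The expected sample sizes and early-termination probabilities also agree with Section 12.2. Against the 0.80 target the margins are 0.003, 0.001 and 0.014.

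**Step 2: worst case.** If a share q cannot respond at all and the rest respond at the alternative rate p1, the effective ORR is p1 × (1 − q). At q = 5% this is 0.40 × 0.95 = 0.38 for lymphoma and 0.25 × 0.95 = 0.2375 for MM. Power through the same boundaries:

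| q | Table 16 | Table 17 | Table 18 |
|---|---|---|---|
| 0 | 0.803 | 0.801 | 0.814 |
| 2% | 0.780 | 0.778 | 0.798 |
| 5% | 0.743 | 0.740 | 0.771 |
| 10% | 0.674 | 0.668 | 0.721 |

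For scale, one subject is 1/27 = 3.7%, 1/32 = 3.1% or 1/40 = 2.5% of a full cohort.

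**Step 3: milder case.** If the affected subjects respond, by CR, at half the rate of the others, the effective ORR is p1 × (1 − q/2). Then q = 10% gives the 5% row: 0.743, 0.740 and 0.771.

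**Step 4: direction of the error.** Each design ends either in success or in the futility region, so lost power reappears there. For Table 16 the chance of ending in futility at the alternative is 1 − 0.803 = 0.197 with q = 0, 1 − 0.743 = 0.257 at q = 5% and 1 − 0.674 = 0.326 at q = 10%. At the null rate, 20% × (1 − q) or 10% × (1 − q), type I error at q = 10% falls to 0.052, 0.036 and 0.046.

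**The case against.** **The power statement is not wrong.** A reader might infer that the designs fail to deliver their stated power. The documents do not support that. Section 12.1 defines p as the response rate of the patients in each cohort. If 40% or 25% is the true rate among those enrolled, including any without measurable disease, power is exactly as stated. A loss arises only if the alternatives describe subjects who can be scored and others enter as well. This stands.

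**No route to PR does not mean no response.** A reader might also take the worst-case rows as the expected effect. CR remains open in Appendix 4, including by marrow clearance, and CR counts in the ORR. This stands, and it makes the rows in step 2 an upper bound on the loss for a given q.

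**The affected group is narrow.** Appendix 4 also covers splenic and hepatic nodules, with a single nodule judged on one diameter. It classes as partial responders those who meet CR except for persistent marrow involvement. Appendix 6 offers FLC and marrow routes. Section 7.6.5 asks for a fresh tumor biopsy from Part 2 lymphoma subjects, though Section 5.2.2 also accepts archival tissue. All this makes q smaller. None of it is an entry rule that sets q to zero. The marrow clause also leaves it unclear how marrow-only lymphoma would be scored, which is a further reason to settle measurability at entry.

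**Futility is non-binding.** Sections 3.3.7 and 3.4 leave stopping to the totality of the data, so a crossed boundary need not end a cohort. The calculation treats each crossing as a stop. This stands: the figures are chances of crossing, not of stopping.

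**Conclusion.** The eligibility gap is real, and it lies in the cohorts with a formal ORR test. It does not make the stated power wrong. It leaves designs with 0.1 to 1.4 percentage points of slack exposed to dilution. In the worst case, where affected subjects never respond, a 2% share costs about 2 points of power, 5% costs 4 to 6 and 10% costs 9 to 13. If they respond at half the rate, 10% costs 4 to 6. The share is an assumption that nothing in the protocol fixes. The power losses assume that the remaining subjects respond at the design alternative.

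If the affected subjects cannot respond, the error is conservative for claims of activity. What increases is the chance that an active drug falls at or below a futility boundary. The point merits correction because entry criteria are fixed in the protocol and the remedy is short.

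**What to change.** In Sections 5.2.1 and 5.2.2 and the synopsis, add for the expansion cohorts:

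- Lymphoma: at least one baseline lesion measurable under the Appendix 4 PR rules, on the CT already required.
- MM: disease measurable by one of the Appendix 6 PR routes, namely M-protein, FLC, or baseline marrow plasma cells of at least 30%.

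Apply the same condition to dose-escalation subjects treated at the MTD/RP2D before they are counted in Tables 16-18, because Sections 3.3.7, 3.4 and 12.2 carry them into those counts. Other dose-escalation subjects may stay exempt.

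Cost: a few patients with non-measurable disease become ineligible for the expansion cohorts. Lymphoma needs no new procedure. For non-secretory MM, Table 6 already requires marrow but not FLC, so a subject qualifying by FLC would need one added test.
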